9.4.3 Electrocardiogram

For the treatment-emergent ECG measurements, a summary of observed values and change from baseline values will be provided at each visit and time point, as applicable, for the following ECG measurements: heart rate (HR; beats per minute [bpm]), PR interval (msec), RR interval (msec), QRS duration (msec), QT interval (msec), and QT corrected for HR intervals (QTcF [msec]).

The number and percentage of subjects meeting threshold analysis criteria during the TE period will be summarized. The threshold analysis criteria are provided in Appendix D. A listing containing individual subject measurements meeting the threshold value criteria at any time point will be provided. This listing will include data from both scheduled and unscheduled visits.

In addition, the number and percentage of subjects by maximum treatment-emergent value of QT/QTcF intervals, categorized as \leq 450 msec, >450 msec and \leq 480 msec, >480 msec and

 \leq 500 msec, and >500 msec, as well as maximum treatment-emergent change from baseline value of QT/QTcF intervals, categorized as \leq 0 msec, >0 and \leq 30 msec, >30 and \leq 60 msec, and >60 msec, will be provided.

ECGs are performed in triplicate. The mean of the ECG measurements will be used as the ECG value for summaries of observed values and change from baseline values. All reported ECG measurements will be used to conduct threshold analyses and to assess maximum treatment-emergent values.

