PGA		X			X	X	X		Recorded in the e-diary ^d ; Section 11.4.1. Subjects should still complete the PGA even if the specified dose is not taken. Day 2: To be completed after the third study drug dose (approximately 24 hours after the first dose). Day 7: Completed after the first study drug dose on Study Day 7 (whether or not this coincides with the date of the Day 7 Visit). Day 14 or EDV: Completed after final study drug dose for subjects still taking study drug on Day 14. Subjects who have discontinued or completed study drug treatment should complete the PGA at home within approximately 24 hours after the last (or presumed last) dose of study drug rather than waiting for their scheduled visit.
Vital signs			X (postdose) ^b		Х	х	Х	Х	Vital signs will be collected after a \geq 5-minute rest (seated or supine) and before any 12-lead ECG assessment or blood sampling; Section 11.5.3.
Standard 12-lead ECG	at discharg	ours after first e or before lea ility, as applic	ving medical		X (4 hours after a dose) ^e	X (4 hours after a dose) ^{e,f}	X	(X)	Required at SFU only if any clinically significant abnormalities were noted on a prior ECG. Standard 12-lead ECGs will be performed in triplicate after a ≥5-minute rest (supine); these will be done after taking vital signs and before any procedures that may affect heart rate (e.g., blood sampling); Section 11.5.4.

Table 3-4Study VX22-548-107: Treatment Period and Safety Follow-up Visit (All Subjects)

Table 3-4Study VX22-548-107: Treatment Period and Safety Follow-up Visit (All Subjects)

Event/Assessment ^a	Day 1	Day 2	Discharge ^b	Day 4 (± 1 day)	Day 7 (± 1 day)	Day 14 (+ 3 days)	End of Dosing Visit ^c	Safety Follow-up Visit Day 28 (± 2 days)	Comments
Symptom-directed PE				As applicable					Symptom-directed PEs will occur at any time during the study if triggered by AEs or if deemed necessary by the investigator; Section 11.5.3.
Focused PE (surgical subjects only)								Х	Assessment of wound healing at the operative site; Section 11.5.3.
Complete PE								(X)	Required at SFU only if a clinical finding during the Treatment Period requires follow up, in which case the subject must have a clinic visit; Section 11.5.3.
C-SSRS			X (postdose) ^b		Х	Х	X		Section 11.5.5
Urine β-hCG						Х	Х	Х	All female subjects of childbearing potential; Section 11.5.2.
Serum chemistry			X (postdose) ^b			Х	X	(X)	Required at SFU only if a clinical finding during the Treatment

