- ^c If a subject discontinues or completes study drug treatment for any reason before Day 14, including AEs (considered treatment discontinuation) or reaching pain resolution (considered treatment completion), an EDV should be scheduled to occur as soon as possible after treatment discontinuation or after pain resolution criteria are met (as applicable), and the Day 14 Visit will not be required. If the EDV occurs within or prior to the Day 7 visit window, the Day 7 Visit will also not be required. Subjects who discontinue or complete study drug treatment before Day 14 will be required to complete the Safety Follow-up Visit. In the unlikely event that the EDV is delayed and occurs 28 days or later following the first dose of study drug, then a separate Safety Follow up Visit will not be required.
- ^d For all e-diary assessments, a paper version will be available as a back-up option.
- ^e Refer to Section 9.6 for instructions on dose and visit scheduling on days of postdose ECGs.
- f Subjects who have their Day 14 Visit after Study Day 14 (per the visit window) and thus are no longer taking study drug will have an ECG any time that day rather than 4 hours postdose.
- ^g For subjects who remain on study drug treatment at Day 14, only 1 dose of study drug should be taken on that day, and it will be the last dose of study drug for these subjects.

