9 STATISTICAL ANALYSIS

9.1 General Considerations

The Schedule of Assessments is provided in Section 3 of the CSP. The precision standards for reporting variables are provided in an internal Biometrics document that specifies the programming rules including the precision for derived variables.

All individual subject data for subjects who have received at least 1 dose of study drug will be presented in individual subject data listings.

Continuous variables will be summarized using the following descriptive summary statistics: the number of subjects (n), mean, standard deviation (SD), median, minimum value (min), and maximum value (max).

Categorical variables will be summarized using counts and percentages.

Baseline value, unless specified otherwise, will be defined as the most recent non-missing measurement (scheduled or unscheduled) collected before the first dose of study drug.

For ECGs, the baseline value will be defined as the average of the most recent non-missing measurements (scheduled or unscheduled) collected before the first dose of study drug, expected to be the triplicate predose measurements on Day 1.

Change (absolute change) from baseline will be calculated as post-baseline value – baseline value.

Treatment-emergent (TE) Period will include the time from the first dose of study drug to the Safety Follow-up Visit or to the completion of study participation (as defined in Section 9.1.7 of the CSP), whichever occurs first.

Unscheduled visits: Unscheduled visit measurements will be included in the analysis as follows:

• In scheduled visit windows per specified visit windowing rules

- In the derivation of baseline
- In the derivation of maximum and minimum values during the TE period, and maximum and minimum change from baseline values during the TE period for safety analyses
- In individual subject data listings as appropriate

Visit windowing rules: The analysis visit windows for protocol-defined PGA entries, which are provided by the subject in a dosing diary, are provided in Appendix A. All safety assessments are analyzed according to their nominal visits.

Outliers: No formal statistical analyses will be performed to detect and/or remedy the presence of statistical outliers.

Multiplicity: Only descriptive analyses will be performed; no statistical hypothesis testing will be performed.

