Table 12-3 Threshold Analysis Criteria for Laboratory Tests (as applicable)

Table 12-4 Threshold Analysis Criteria for ECGs

Parameter	Threshold Analysis	Comments
HR	Bradycardia <50 bpm <45 bpm Decrease from baseline ≥10 bpm Decrease from baseline ≥20 bpm <50 bpm and decrease from baseline ≥10 bpm <50 bpm and decrease from baseline ≥20 bpm	Per HV grade 2, 3, plus shift change
	Tachycardia >100 bpm >115 bpm >130 bpm Increase from baseline ≥10 bpm Increase from baseline ≥20 bpm >100 bpm and increase from baseline ≥10 bpm >100 bpm and increase from baseline ≥20 bpm	Per HV grade 1, 2, 3, plus shift change
PR	≥240 ms ≥300 ms ≥200 ms and increase from baseline ≥40 ms ≥200 ms and increase from baseline ≥100 ms	
QRS	>110 ms >160 ms Increase from baseline ≥20 ms Increase from baseline ≥40 ms	
QTc	>450 to <500ms (Male) or >470 to <500ms (Fema ≥500 ms Increase from baseline Increase from baseline >10 ms Increase from baseline >20 ms Increase from baseline >40 ms Increase from baseline >60 ms	ale) To be applied to any kind of QT correction formula.

Parameter	Threshold Analysis	Comments
Pulse Rate	Same as above in ECG category	
SBP increased	>140 mmHg	
	>160 mmHg	
	>10 mmHg increase from baseline	
	>20 mmHg increase from baseline	
	>140 mmHg & >10 mmHg increase from baseline	
	>140 mmHg & >20 mmHg increase from baseline	
	>160 mmHg & >10 mmHg increase from baseline	
	>160 mmHg & >20 mmHg increase from baseline	
SBP decrease	<90 mmHg	Per HV grade 1, 3, plus shift change
	<80 mmHg	
	>10 mmHg decrease from baseline	
	>20 mmHg decrease from baseline	
	<90 mmHg and >10 mmHg decrease from baseline	
	<90 mmHg and >20 mmHg decrease from baseline	
	<80 mmHg and >10 mmHg decrease from baseline	
	<80 mmHg and >20 mmHg decrease from baseline	
DBP increased	>90 mmHg	
	>100 mmHg	
	>5 mmHg increase from baseline	
	>10 mmHg increase from baseline	
	>90 mmHg and >5 mmHg increase from baseline	
	>90 mmHg and >10 mmHg increase from baseline	
	>100 mmHg and >5 mmHg increase from baseline	
	>100 mmHg and >10 mmHg increase from baseline	
DBP decreased	<60 mmHg	
	<45 mmHg	
	>5 mmHg decrease from baseline	
	>10 mmHg decrease from baseline	
	<60 mmHg and >5 mmHg decrease from baseline	
	<60 mmHg and >10 mmHg decrease from baseline	
	<45 mmHg and >5 mmHg decrease from baseline	
	<45 mmHg and >10 mmHg decrease from baseline	
Oxygen saturation	<88%	
decreased	<95% and decrease from baseline $>5%$ of absolute	
	oxygen saturation	

 Table 12-5
 Threshold Analysis Criteria for Vital Signs

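### Cheap improvement: SAP 9.4.3 counts ECG changes from baseline on single tracings against an averaged baseline; add a labelled triplicate-mean count and state the unit of the maximum-change table

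*SAP*

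**What the plan says.** SAP 9.1 defines the ECG baseline as an average, expected to be that of the Day 1 predose triplicate. SAP 9.4.3 then uses two units for post-dose values:

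- By-visit tables: "The mean of the ECG measurements will be used as the ECG value for summaries of observed values and change from baseline values".
- Outlier tables: "All reported ECG measurements will be used to conduct threshold analyses and to assess maximum treatment-emergent values".

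Table 12-4 in SAP Appendix D mixes absolute limits with change criteria. For QTc the change criteria are any increase and increases above 10, 20, 40 and 60 msec; one row reads "Increase from baseline >20 ms". Heart rate, PR and QRS have change criteria too, some of them combining a level with a change. SAP 9.4.3 also plans a separate table of the largest QT/QTcF change, banded at 0, 30 and 60 msec. For follow-up of flagged values it adds: "A listing containing individual subject measurements meeting the threshold value criteria at any time point will be provided".

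**The concern.** A change criterion compares a post-dose value with a baseline. Here the baseline is smoothed over three tracings and the post-dose value is not. One stray tracing is enough to flag a subject whose triplicate as a whole has not moved.

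ECGs are part of the primary endpoint, the study has one arm, and all analyses are descriptive. The reader of a count of QTcF rises above 20 msec has no concurrent group showing how many to expect from measurement noise. The Table 12-4 counts cannot show whether a flag reflects one tracing or a shift in all three.

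**Working it through.** **The plan's own figure.** The only numerical design figure is the chance of seeing an AE at least once in 250 subjects. It reproduces: 1 − 0.99^250 = 91.9% and 1 − 0.98^250 = 99.4%, against the stated 92% and 99%. It is unaffected by this point. No expected ECG outlier rate is given.

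**Direction (no assumption needed).** Let B be the baseline and x1, x2, x3 the tracings at one time point. Then max(x1, x2, x3) − B ≥ mean(x1, x2, x3) − B, and the mirror image holds for decreases. The same is true of the Table 12-4 criteria that combine a level with a change: if the mean meets both parts, the most extreme tracing does too. Every subject flagged on a mean is therefore also flagged on a tracing.

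**Size (SDs assumed).** The documents give no ECG variability. The model has no drug effect and normal errors:

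- baseline = visit effect + mean of 3 tracing errors;
- post-dose tracing = visit effect + tracing error, 3 tracings at each of K times;
- a subject is flagged if the largest tracing, or the largest triplicate mean, exceeds baseline by more than the cut-off.

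K = 3 follows Protocol Table 3-4: one early ECG, Day 7, and Day 14 or the End of Dosing Visit (EDV). K falls to 2 for early stoppers ("If the EDV occurs within or prior to the Day 7 visit window, the Day 7 Visit will also not be required") and rises to 4 only with a follow-up ECG ("Required at SFU only if any clinically significant abnormalities were noted on a prior ECG").

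QTcF rise above 20 msec, K = 3, 400,000 simulated subjects, single tracing / triplicate mean (%):

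| Visit SD (msec) | Tracing SD 1 | Tracing SD 3 | Tracing SD 5 | Tracing SD 7 |
|---|---|---|---|---|
| 5 | 1.00 / 0.68 | 2.93 / 1.03 | 8.14 / 1.87 | 17.44 / 3.56 |
| 6 | 3.22 / 2.48 | 6.40 / 3.04 | 12.63 / 4.28 | 21.75 / 6.28 |
| 8 | 10.93 / 9.44 | 15.52 / 10.13 | 22.04 / 11.46 | 30.01 / 13.40 |

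- Hand check at 5/3. One mean-based change has SD √(2×25 + 2×9/3) = √56 = 7.48, so P(>20) = P(Z > 2.67) = 0.38%. Three times give at most 3 × 0.38 = 1.1%, against 1.03% simulated. One single-tracing change has SD √(2×25 + 9 + 9/3) = √62 = 7.87, so P(>20) = 0.55%. Nine tracings give at most 5.0%, against 2.93% simulated. Numerical integration gives 2.95 / 1.04.
- In subjects out of 250: 0.0100 × 250 = 2.5 against 0.0068 × 250 = 1.7 at the low end; 0.3001 × 250 = 75 against 0.1340 × 250 = 33.5 at the high end.
- Share of flagged subjects not flagged on the mean: 1 − 9.44/10.93 = 14% (8/1) to 1 − 3.56/17.44 = 80% (5/7).
- K = 2: 0.71 / 0.48 (5/1) to 23.25 / 10.02 (8/7). K = 4: 1.29 / 0.90 to 35.06 / 16.18.

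Other cut-offs over the same SDs, K = 3: above 10 msec, 22–64% against 18–41%; above 40 msec, 0.00–1.33% against 0.00–0.23%; above 60 msec, at most 0.01% against 0.00%. With both SDs at 12 msec, the figures above 60 msec become 5.2 against 0.8 of 250 (2.1% against 0.3%). Heart-rate rise of 20 bpm or more: 0.12 / 0.07% (visit SD 4, tracing SD 1 bpm) to 18.56 / 10.73% (8/4).

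**The maximum-change table.** SAP 9.4.3 names maximum values and maximum changes separately. Its mean sentence covers changes from baseline; its all-measurements sentence covers threshold analyses and maximum values. The table of largest changes fits either. The only >30 msec cut is in this table, so a gap there exists only if it is built on single tracings: 0.01–8.3% against 0.00–2.3% under the same assumptions.

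**The case against.** The best defence is that the two units are deliberate. Means describe the average course, and single tracings give a sensitive screen. In a descriptive safety study that is coherent and executable, no stopping rule uses the counts, and averaging could dilute a real excursion. By-visit mean changes, a listing of flagged measurements and central cardiologist reading of all traces are already planned. The protocol's on-study QTcF check uses the triplicate median with repeat ECGs. All of this stands. It is why the screen should be kept and why this is an improvement, not the correction of an error.

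Means are no cure either. They still flag 18–41% of subjects above 10 msec with no drug effect, because the maximum is taken over several visits. A systematic baseline shift, for example because the surgical baseline is taken after surgery, would move both counts. With a 10 msec downward shift at SDs 8/5, the >20 msec figures fall from about 22% and 11.5% to 4.7% and 1.7%. Averaging does not remove that.

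Three stronger readings are tempting, and the documents do not support them:

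- That no planned summary count separates a stray tracing from a shifted triplicate. The maximum-change QT/QTcF table may already be on means. The SAP 9.1 phrase "maximum and minimum change from baseline values during the TE period for safety analyses" does not settle this, because it concerns the use of unscheduled visits, not averaging.
- That noise can only raise the count relative to the truth. The inequality is exact only against triplicate means on the same data. Against noise-free values, baseline error can hide a subject's real exceedance.
- That the >60 msec row is immune. That depends on the assumed SDs.

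**Conclusion.** The point holds as a low-cost improvement. The Table 12-4 change criteria are applied to single tracings against an averaged baseline, and the resulting counts can never be below the triplicate-mean counts. That direction is certain.

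The size is not. For QTcF above 20 msec it runs from under one extra subject in 250 to about 41 (75 − 33.5), assuming normal errors, no drug effect, three post-dose times and SDs of 5–8 msec (visit) and 1–7 msec (tracing). Larger SDs would widen the gap and extend it to >60 msec. The unit of the maximum-change table is ambiguous, and any statement about >30 msec depends on how that is resolved. Absolute thresholds use no baseline and are not at issue. A reader might infer that the safety conclusions would be wrong as planned; the documents do not support that.

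**What to change.** In SAP 9.4.3:

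1. Add the Table 12-4 change-from-baseline counts on the mean of the tracings at each time point, at least for QTcF and heart rate, including criteria that combine a level with a change.
2. Label the existing change counts 'any tracing'.
3. State that the maximum-change QT/QTcF table uses the triplicate mean, or present both units, labelled.
4. Keep the any-tracing rule for absolute thresholds and maximum values.

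The triplicates are already collected and already averaged for the by-visit tables, so no new data are needed. The cost is a few sentences and some extra output. Table 12-4 has 17 rows involving a change (8 heart rate, 2 PR, 2 QRS, 5 QTc), 13 of them for heart rate and QTc. SAP 9.5 repeats safety summaries for surgical subjects, and for non-surgical subjects if they are at least 10% of the total. Readers will see two counts per change criterion, so the labels must be clear.

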9.4.4 Vital Signs

For the treatment-emergent vital signs measurements, the observed values and change from baseline values will be summarized at each visit. The following vital signs parameters will be summarized: systolic and diastolic blood pressure (mm Hg), pulse rate (beats per minute), body temperature (°C), respiratory rate (breaths per minute), and oxygen saturation (%).

The number and percentage of subjects meeting threshold analysis criteria during the TE Period will be summarized. The threshold analysis criteria are provided in Appendix D.

In addition, a listing containing individual subject vital signs values will be provided. This listing will include data from both scheduled and unscheduled visits.

9.4.5 Physical Examination

Physical examination (PE) results will be presented in an individual subject data listing only.

9.4.6 Columbia-Suicide Severity Rating Scale

For each event category on the C-SSRS (suicidal ideation, suicidal behavior, suicidal ideation or behavior, self-injurious behavior without suicidal intent), the proportion of subjects with at least one event in the category during the TE Period will be summarized. C-SSRS results for subjects with responses of "Yes" at any visit will also be presented in an individual subject data listing.

9.5 Subgroup Analyses

All summaries of safety, effectiveness, and use of rescue medication will be presented for surgical subjects. These summaries will also be presented for non-surgical subjects if they constitute at least 10% of the total subjects; otherwise, data for non-surgical subjects will be presented in listings only. Due to the underlying differences in the subgroup populations and potentially limited sample sizes in the non-surgical subgroup, these analyses should be interpreted with caution.

Additionally, the proportion of subjects receiving fentanyl citrate, the median dose, and time from last administration of fentanyl citrate to the first dose of study drug among surgical subjects will be summarized in a separate table.

10 SUMMARY OF INTERIM AND IDMC ANALYSES

Interim analyses may be performed during the study. If these occur, the timing and details of the interim analyses will be documented in the SAP prior to its finalization.

11 **REFERENCES**

Not applicable.

12 LIST OF APPENDICES

Appendix A: Analysis Visit Windows for Effectiveness Assessments

Table 12-1 Analysis Visit Windows for Effectiveness Assessments			
Assessment	Visit/Timepoint	Target Study Day	Analysis Visit Window (in study days/timepoints)
PGA	EDV	After treatment completion/disconti nuation	First assessment between 0 and 48 hours after subject's last dose of VX-548

Note: If no PGA measurement is available within the EDV visit window, PGA at EDV will be imputed with the previous PGA measurement, if available.

Appendix B: Imputation Rules for Missing Medication and Dates/Times

Imputation rules for missing or partial medication start/stop dates are defined below:

- 1. Missing or partial medication start date and time:
 - a. If hour and/or minute are missing, do not impute.
 - b. If day is missing, use the first day of the month.
 - c. If day and month are both missing, use the first day of the year.
 - d. If day, month and year are all missing, use a date before the first dose date.
- 2. Missing or partial medication stop date and time:
 - a. If hour and/or minute are missing, do not impute.
 - b. If day is missing, use the last day of the month.
 - c. If day and month are both missing, use the last day of the year.
 - d. If day, month and year are all missing, assign 'continuing' status to stop date.

With missing or partial medication start times, only use the imputed start date to categorize the prior and/or concomitant medication as described in Table 12-2. If hour and/or minute of the first dose time are missing, only use the first dose date to categorize the prior and/or concomitant medication. Imputation of missing and/or partial dates for non-pharmacological treatments/procedures will follow the same imputation rule.

Table 12-2 Prior and/or Concomitant Categorization of a Medication

	Medication Stop Date	
	First Dose Date/Time of Study Drug	≥ First Dose Date/Time and ≤ End Date of TE
Medication Start Date		Period
< First dose date/time of study drug	Р	PC
\geq First dose date/time and \leq end date of TE period	-	С

C: Concomitant; P: Prior

Appendix C: Imputation Rules for Missing AE Dates and Times

Imputation rules for missing or partial AE start dates and times are defined below:

If Hour and/or Minute of AE start time are missing, do not impute:

- If the AE start date is before the first dose date, the AE will be classified as a pretreatment AE.
- If the AE start date is on or after the first dose date, the AE will be classified as a TEAE.

If only Day of AE start date is missing:

- If the AE start year and month are the same as that for the first dose date, then:
 - If the full (or partial) AE end date is NOT before the first dose date or AE end date is missing, then impute the AE start day as the day of the first dose date
 - Otherwise, impute the AE start day as 1.
- Otherwise, impute the AE start day as 1.

Compare the imputed AE start date with the TE period to determine whether the AE is a pretreatment AE or TEAE.

If Day and Month of AE start date are missing:

- If AE start year is the same as the year of the first dose date, then:
 - If the full (or partial) AE end date is NOT before the first dose date or the AE end date is missing, then impute the AE start month and day as the month and day of the first dose date;
 - Otherwise, impute the AE start month as January and the day as 1.
- Otherwise, impute the AE start month as January and the day as 1.

Compare the imputed AE start date with TE period to determine whether the AE is a pretreatment AE or TEAE.

If Year of AE start date is missing:

If the year of AE start is missing or AE start date is completely missing, then query the site with no imputation. Compare the full (or partial) AE end date to the first dose date. If the AE end date is before the first dose date, then the AE should be considered as a pretreatment AE. Otherwise, the AE will be considered as a TEAE.

If Hour and/or Minute of first dose time are missing:

- If the AE start date is before the first dose date, the AE will be classified as a pretreatment AE.
- If the AE start date is on or after the first dose date, the AE will be classified as a TEAE.

A missing or partially missing AE end date will not be imputed.

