9 STUDY IMPLEMENTATION

9.1 Study Design

This is a Phase 3, single-arm study evaluating the safety and effectiveness of VX-548 in treating acute pain (Figure 9-1 [surgical subjects] and Figure 9-2 [non-surgical subjects]).

Figure 9-1 VX22-548-107 Study Design (Surgical Subjects)

NPRS: numeric pain rating scale; VRS: verbal categorical rating scale

Notes: After surgery completion, a subject will be assigned to treatment if (1) the subject requests the first dose of study drug for pain relief, (2) the subject's pain is moderate or severe on the VRS, and (3) the subject's pain is ≥4 on the NPRS. If a subject does not meet the VRS and NPRS criteria within the protocol-specified, procedure-specific time period, the subject will not be eligible for this study. Figure is not drawn to scale.

Figure 9-2 VX22-548-107 Study Design (Non-surgical Subjects)

NPRS: numeric pain rating scale; VRS: verbal categorical rating scale

Notes: After completion of screening assessments and confirmation of eligibility, a subject will be assigned to treatment if (1) the subject's pain is moderate or severe on the VRS, and (2) the subject's pain is ≥4 on the NPRS. Figure is not drawn to scale.

Surgical Subjects

On Day 1, subjects will undergo a scheduled ambulatory surgical procedure with pain that is expected to last for at least 72 hours and that is expected to require no more than a short-term (i.e., <24-hour) admission. After surgery completion, a subject will be assigned to treatment if (1) the subject requests the first dose of study drug for pain relief, (2) the subject's pain is moderate or severe on the VRS, and (3) the subject's pain is \geq 4 on the NPRS. If a subject does not meet the VRS and NPRS criteria within the protocol-specified time period for the surgical procedure they underwent (e.g., 4 hours for most procedures; Section 8.1), the subject will not be eligible for this study.

Non-surgical Subjects

On Day 1, after completion of screening assessments and confirmation of eligibility, a subject will begin treatment if (1) the subject's pain is moderate or severe on the VRS, and (2) the subject's pain is \geq 4 on the NPRS. For a subject to be eligible, their pain must have been ongoing for \leq 48 hours at presentation.

All Subjects

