12 STATISTICAL ANALYSIS

12.1 Sample Size and Power

Approximately 250 subjects are planned to be enrolled. With 250 subjects, there is a 92% probability of observing an AE in at least 1 subject if the true incidence is 1% and a 99% probability of observing an AE in at least 1 subject if the true incidence is 2%.

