13.1.1.3 Documentation of Adverse Events

All AEs will be collected in source documents from the time the ICF is signed until completion of study participation (Section 9.1.7).

All subjects will be queried, using nonleading questions, about the occurrence of AEs at each study visit. When possible, a constellation of signs and/or symptoms will be identified as 1 overall event or diagnosis. All AEs for enrolled subjects will be recorded in source documents. AEs for subjects who are screened but not subsequently enrolled will be recorded only in the subject's source documents. The following data will be documented for each AE:

- Description of the event
- Classification of "serious" or "nonserious"
- Date of first occurrence and date of resolution (if applicable)
- Severity
- Causal relationship to study drug(s)
- Action taken
- Outcome
- Concomitant medication or other treatment given

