9.4.1 Adverse Events

AEs will be coded according to MedDRA. For analysis purposes, AEs will be classified as pretreatment AEs and TEAEs as follows:

Pretreatment AEs: AEs that occurred before the first dose of study drug

Treatment-emergent AEs: AEs that worsened or started after the first dose of study drug through the end of the TE Period

For AEs with completely missing or partial start dates/times, if there is no clear evidence that the AEs started before or after the first dose of study drug, the AEs will be classified as TEAEs.

Imputation rules for missing or partial AE start dates/times are defined in Appendix C.

AE summary tables will be presented only for TEAEs, and will include the following:

- All TEAEs
- TEAEs by strongest relationship
- TEAEs by maximum severity
- TEAEs leading to treatment discontinuation
- TEAEs leading to treatment interruption
- Related TEAEs
- Serious TEAEs

- Related serious TEAEs
- TEAEs leading to death

Summaries will be presented by MedDRA SOC and PT using frequency counts and percentages (i.e., number and percentage of subjects with an event). When summarizing the number and percentage of subjects with an event, subjects with multiple occurrences of the same AE or a continuing AE will be counted once, and only the maximum severity level will be presented in the severity summaries, and the strongest relationship level in the relationship summaries.

All AEs, including pretreatment AEs and TEAEs, will be presented in an individual subject data listing. In addition, a listing containing individual subject AE data for TEAEs leading to treatment discontinuation, TEAEs leading to treatment interruption, SAEs, and all deaths will be provided separately.

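### SAP Appendix C counts an adverse event on the first-dose date with no start time as treatment-emergent even when it is known to have begun before dosing, contrary to SAP 9.4.1

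*SAP*

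**What the plan says.** SAP 9.4.1 defines treatment-emergent adverse events (TEAEs) as "AEs that worsened or started after the first dose of study drug through the end of the TE Period". For events with missing or partial start dates or times, it applies a TEAE default only where nothing clearly shows whether the event came before or after the first dose. It then refers to Appendix C for the detailed rules.

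Appendix C, in the branch for a missing start hour or minute, says: "If the AE start date is on or after the first dose date, the AE will be classified as a TEAE". That branch does not repeat the 9.4.1 condition. It does not look at when the event ended, although the branches for a missing day, month or year do consult the end date.

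Protocol 13.1.1.3 collects adverse events from consent onward. The timing item in its list of data for each event is "Date of first occurrence and date of resolution (if applicable"; no clock time is listed. Protocol 9.6 requires the time of each study drug dose, and Protocol 9.5 the time of each in-clinic medication.

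For the sequence of events, Protocol 9.1 says: "On Day 1, subjects will undergo a scheduled ambulatory surgical procedure". The first dose follows surgery once the subject asks for it and meets the pain criteria.

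**The concern.** For a surgical subject, admission, anesthesia, surgery, recovery and first dose usually fall on one calendar date, so a date alone cannot order an event relative to the dose. Take nausea noted in the recovery room before any VX-548 and entered with a date only. Source notes show that it came first. Under 9.4.1 it is a pretreatment event; under Appendix C it is a TEAE. A programmer following Appendix C would count it.

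TEAEs are part of the primary endpoint. The study has one arm and "no statistical hypothesis testing will be performed", so no comparator shows the perioperative background. Events that began before exposure would enter the overall TEAE table, the severity table and the system organ class and preferred term tables, and a reader of those tables could not pick them out.

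**Working it through.** **1. The plan's own figures.** Protocol 12.1 says "Approximately 250 subjects are planned to be enrolled" and gives a 92% chance of seeing at least one event at a true incidence of 1%, and 99% at 2%. With P = 1 − (1 − p)^250, p = 0.01 gives 0.9189 and p = 0.02 gives 0.9936. Both reproduce. Neither depends on the TEAE rule.

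**2. The two rules side by side, for an event dated on the first-dose date with no start time.**

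| What is known about order | SAP 9.4.1 | Appendix C |
|---|---|---|
| Clearly began before the dose and did not worsen after it | Pretreatment | TEAE |
| Clearly began after the dose | TEAE | TEAE |
| Unknown | TEAE | TEAE |

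They differ only in the first row. An end date cannot settle that row, because an event that starts on the first-dose date cannot end on an earlier date. An end time, an onset time or an explicit flag is needed.

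**3. Illustrative size.** The documents give no rate of pre-dose events or of missing times. Assumptions:
- surgical share s = 90% (SAP 9.5 allows for a non-surgical group below 10%);
- share of surgical subjects with a pre-dose event on the first-dose date, q = 5% to 20%;
- share of those events with no start time, m = 25% to 100%;
- true any-TEAE rate t = 35%;
- pre-dose events independent of true TEAEs.

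Misclassified share = s × q × m. Reported rate = t + (1 − t) × s × q × m.

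| q | m | s × q × m | Subjects of 250 | Reported rate | Excess (points) |
|---|---|---|---|---|---|
| 5% | 25% | 0.01125 | 2.8 | 35.7% | 0.7 |
| 10% | 50% | 0.045 | 11.3 | 37.9% | 2.9 |
| 20% | 100% | 0.18 | 45 | 46.7% | 11.7 |

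For the same three rows, the excess is 0.9, 3.6 and 14.4 points if t = 20%, and 0.6, 2.2 and 9.0 points if t = 50%.

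**4. One preferred term.** With a true rate of 2% and 5% of surgical subjects having that event before dosing, the reported rate is 0.02 + 0.98 × 0.9 × 0.05 × m. This gives 3.1% at m = 25%, 4.2% at 50% and 6.4% at 100%.

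**5. Complete times.** If m = 0, the excess is 0.

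**The case against.** The strongest reply is that times may well be collected. Appendix C is written for missing times, which suggests that a time field exists, and SAP section 4 says the plan rests on the approved eCRF and its completion guidelines. The protocol's list does not prove that no time is captured. This stands: with a time field, only records that lack the time are affected.

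Second, 9.4.1 already limits the default to unclear cases. That is also true, but Appendix C does not carry the limit into the branch that applies. What remains is a conflict between two parts of one SAP.

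Third, the pool of events is smaller than it may look. Exclusion criteria 28 and 29 remove subjects with any surgical complication during the procedure, or a medical complication judged to preclude treatment, before dosing. If dosing passes midnight, a date-only event on the surgery date is pretreatment. A reader might infer that inclusion criterion 6 bounds the time to first dose at 4 hours (12 after regional anesthesia). It bounds the qualifying pain report, not the dose.

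Fourth, the default is conservative, the analysis is descriptive, and the SAP also tabulates TEAEs by relationship, lists every event and summarizes surgical subjects separately. This softens the effect, since events judged unrelated drop out of the related-TEAE table. It does not correct the overall TEAE incidence or the preferred term tables.

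**Conclusion.** The inconsistency stands on the text: followed as written, Appendix C can turn an event known to precede dosing into a TEAE, against the SAP's own definition. The direction is over-counting.

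The documents do not give the size. The range of about 0.7 to 11.7 points on an assumed 35% rate (about 3 to 45 of 250 subjects) rests wholly on the assumptions listed above and is an illustration, not an estimate.

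A reader might go further and infer that every adverse event on the day of surgery becomes a TEAE, or that the rate is inflated by as much as 45/250 = 18 points. The documents support neither. The rule applies only where the time is missing and the event shares the first-dose date. The 18-point figure also needs every pre-dose event to lack a time and no affected subject to have a true TEAE.

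This is worth correcting because the endpoint is primary, there is no control arm and the correction is cheap. It does not threaten the study.

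**What to change.** - **Data capture.** In Protocol 13.1.1.3 and the eCRF, require an onset time or a before/after-first-dose flag for every adverse event that starts on the first-dose date. If the eCRF already captures this, confirm it and say so in the SAP.
- **Appendix C.** In the missing-time branch, first apply that field, then the 9.4.1 test of clear evidence, then the event's end date and time where recorded. Default to TEAE only when the order is truly unknown. State that an event that began before dosing and worsened afterwards remains a TEAE, as 9.4.1 defines.
- **Optional.** Report how many TEAEs were classified by the default. This is preferable to a sensitivity analysis that drops all date-only Day 1 events, which would also remove genuine post-dose events.

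The cost is at most one eCRF field for one date, a few sentences in Appendix C and, if wanted, one table row. If the eCRF can no longer change, the Appendix C wording can still be amended before database lock, as SAP section 4 allows.
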